Although acne occurs on the face *and* trunk, efficacy assessment by IGA will be limited to the face as that is the most frequent site of involvement. However, the study product may be applied to all affected areas during this clinical trial.

Inflammatory and noninflammatory lesions on the face will be counted and reported separately. All lesions on the face, including the nose should be counted.

Subjects will also be asked a series of patient-reported outcome questions and will be asked to consent to optional photographs of the treated lesions.

Throughout both phases, subjects will be queried regarding adverse events (AEs), concurrent medical history and concomitant medication usage.

Subject Population:

Male or female at least 18 years of age with a clinical diagnosis of mild to severe facial Acne Vulgaris.

Inclusion Criteria:

1. Male or female, at least 18 years of age;
2. A clinical diagnosis of mild to severe facial Acne Vulgaris; Subjects may also have acne at other body sites;
3. Screening and Baseline IGA score ≥ 2 (greater than or equal to 2);
4. Willing to refrain from using any topical or systemic treatments for inflammatory skin disease, other than the investigational product;
5. Candidate for topical treatment of Acne;
6. If a cleanser, moisturizer or sunscreen is needed during the study, Subjects must be willing to use only allowed cleansers, moisturizers, sunscreens, or moisturizer/sunscreen combination products. If the subject wears makeup they must agree to use non-comedogenic makeup.
7. Females of child-bearing potential must have a negative urine pregnancy test within 48 hours prior to the first drug administration;
8. Females of child-bearing potential must be willing to use 2 methods of contraception deemed adequate by the investigator (for example, oral contraceptive pills plus a barrier method) through the trial and for 1 month thereafter to be eligible for, and continue participation in, the study;
9. Ability to complete the study in compliance with the protocol, including agreement in writing to apply study product only to the assigned areas; and
10. Ability to understand and provide written informed consent.

Exclusion Criteria:

1. Any underlying disease(s) or some other dermatological condition of the face that requires the use of interfering topical or systemic therapy or makes evaluations and lesion count inconclusive;
2. Use of androgen receptor blockers (such as spironolactone or flutamide);

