6 STUDY OBJECTIVES

6.1 Primary Objectives

Part A

1. Determine whether the optimum frequency of topical application of BMX-010 0.03% is once per day or twice per day for a treatment interval of 7 to 28 days.
2. Determine whether the optimum frequency of topical application of BMX-010 0.1% is once per day or twice per day for a treatment interval of 7 to 28 days.
3. Determine if BMX-010 cream or gel provides better efficacy.
4. Evaluate the efficacy of BMX-010 0.03% in treatment of Acne Vulgaris.
5. Evaluate the efficacy of BMX-010 0.1% in treatment of Acne Vulgaris.

Part B

1. Evaluate the efficacy of BMX-010 compared to placebo in a randomized, double-blind trial.
2. Determine the percent of subjects showing a 2 grade improvement in IGA score after treatment with BMX-010 compared to Placebo.
3. Determine the percent of subjects showing a 2 grade improvement in IGA score with full or partial clearing (final IGA score of 1 or 0) after treatment with BMX-010 compared to Placebo.
4. Determine the time to full clearing of Acne Vulgaris after initiation of treatment with BMX-010.

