7.2.1 Stopping Rules

The following stopping criteria will be implemented:

1. Subject stopping criteria: If a subject experiences an AE that is deemed by the clinical center Principal Investigator to be at least “possibly” drug-related and is Grade ≥ 2 in severity (using the Common Terminology Criteria for Adverse Events (CTCAE v 5), that subject will be withdrawn from dosing, return for all scheduled evaluation visits, and be followed until the AE resolves or stabilizes.

2. Cohort stopping criteria: If 1 subject in a cohort experiences an AE that is deemed by the clinical center Principal Investigator to be probably or definitely drug-related and is Grade ≥ 3 in severity by CTCAE, or if 2 subjects in a cohort experience AEs that are deemed by the clinical center Principal Investigator(s) to be at least “possibly” drug-related and are Grade $>/= 3$ in severity by CTCAE, dosing further subjects will be suspended until data is reviewed by the sponsor.
3. Dose stopping criteria: If the Acne Vulgaris is deemed as cleared by the study investigator (IGA=0), the subject will be instructed to stop dosing or continue based on the discretion of the clinical center investigator. Acne Vulgaris should be considered clear if it is not showing any inflammatory signs of disease. If it is decided by the local investigator to stop drug treatment, the clinical center investigator will determine which of the following scenarios will be implemented :
 - The subject should return to the clinical center weekly for further assessment.
 - The subject should return the following week to complete the end of study (Day 43) follow up visit.

If the subject is still in the study, and the Acne Vulgaris returns, the subject should contact the clinical center and resume treatment (through Day 28) and weekly visits until the planned Day 43.

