8 SELECTION AND WITHDRAWAL OF SUBJECTS

8.1 Inclusion Criteria

1. Male or female, at least 18 years of age;
2. A clinical diagnosis of mild to severe facial Acne Vulgaris; Subjects may also have acne at other body sites;
3. Screening and Baseline IGA score ≥ 2 (greater than or equal to 2);
4. Willing to refrain from using any topical or systemic treatments for inflammatory skin disease, other than the investigational product;
5. Candidate for topical treatment of Acne;
6. If a cleanser, moisturizer or sunscreen is needed during the study, Subjects must be willing to use only allowed cleansers, moisturizers, sunscreens, or moisturizer/sunscreen combination products. If the subject wears makeup they must agree to use non-comedogenic makeup.
7. Females of child-bearing potential must have a negative urine pregnancy test within 48 hours prior to the first drug administration;
8. Females of child-bearing potential must be willing to use 2 methods of contraception deemed adequate by the investigator (for example, oral contraceptive pills plus a barrier method) through the trial and for 1 month thereafter to be eligible for, and continue participation in, the study;
9. Ability to complete the study in compliance with the protocol, including agreement in writing to apply study product only to the assigned areas; and
10. Ability to understand and provide written informed consent.

8.2 Exclusion Criteria:

1. Any underlying disease(s) or some other dermatological condition of the face that requires the use of interfering topical or systemic therapy or makes evaluations and lesion count inconclusive;
2. Use of androgen receptor blockers (such as spironolactone or flutamide);
3. Severe cystic acne, acne conglobata, acne fulminans, or secondary acne;
4. Use of phototherapy devices, energy-based devices, adhesive cleansing strips, or cosmetic procedures (e.g., facials, peeling, comedo extraction) in the past week;
5. Presence of beard or excessive facial hair at Screening which would interfere with the study treatments or study assessments and refusal to remove for duration of study;
6. Prior or current concomitant therapies that would interfere with assessments in the study;
7. Subjects with any underlying disease that the Investigator deems uncontrolled, and poses a concern for the subject's safety while participating in the study;

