11.1 IGA

The Investigator Global Assessment (IGA) is a five scale (0 to 4) static evaluation of overall Acne Vulgaris severity (as described below). The change in IGA scores from Baseline through the final follow up visit will be assessed as endpoints in the study.

Drug treatment and efficacy assessment by IGA will be limited to the face. For a score of Clear, residual hyperpigmentation and erythema may be present.

Grade	Description
0 = Clear	No papules and/or pustules; no erythema
1 = Minimal	Rare papules and/or pustules; faint, up to but not including mild erythema
2 = Mild	Few papules and/or pustules; mild erythema
3 = Moderate	Pronounced number of papules and/or pustules, but less than numerous papules and/or pustules; moderate erythema
4 = Severe	Numerous papules and/or pustules, occasionally with confluent areas of inflamed lesions; moderate to severe erythema

There is no single, standardized grading system for severity of acne [20].

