40. US Department of Health and Human Services Food and Drug Administration Center for Drug Evaluation and Research (CDER). Acne Vulgaris: Establishing Effectiveness of Drugs Intended for Treatment Guidance for Industry. Rockville, MD: Office of Communications, Division of Drug Information. May 2018.
<https://www.fda.gov/downloads/Drugs/Guidances/UCM071292.pdf>

19 Appendix A: Patient Reported Outcome (PRO) Questions

Weekly Visit

1. How often are you applying the study drug?
 - Once a Day
 - Twice A Day
2. Did you apply the study product as instructed?
 - Yes
 - No
 - If no: clarify with comments
3. Would you like to apply the study drug more often?
 - Yes
 - No
4. Do you feel that your quality of life has improved from using the study drug?
 - Yes
 - No
5. How would you assess the change in your rash since your previous visit?
 - Worse
 - No change
 - A little better
 - Definitely better
 - Drastically better
 - Clear

**Clearing Questions- only to be asked if the Acne Vulgaris has cleared or partially cleared.
Indicate [] N/A if no clearing has occurred**

1. On approximately what date did the Acne Vulgaris clear?
2. Have any of your previously cleared lesion(s) come back? Yes/No
 - a. If Yes, on what date did it come back?
 - b. If Yes, where did it come back?
 - i. Same area as before
 - ii. New area, specify:

The following questions are for the last visit only

1. Do you feel that your quality of life has improved from using the study drug?
 - Yes
 - No

2. How would you assess the change in your rash since your previous visit?
 - Worse
 - No change
 - A little better
 - Definitely better
 - Drastically better
 - Clear

Clearing Questions- only to be asked if the rosacea has cleared or partially cleared.
Indicate [] N/A if no clearing has occurred

1. On approximately what date did the rosacea clear? _____

2. Have any of your previously cleared lesion(s) come back?

- Yes
- No

If Yes, on what date did it come back?

If Yes, where did it come back?

- Same area as before
- New area, specify:

Color Questions

1. Do you have any concerns about the color of the study product?
 - No concerns

- Mild concerns
- Major concerns

2. Did the study product stain (meaning the color stayed on after washing) your clothing/bedsheets, etc? Yes/No

20 Appendix B: Phone Follow-up Questions

1. What is the current status of your Acne?
2. Are you currently on any medications or treatments for controlling your Acne? If yes, obtain list.

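### The Appendix A questions on change, clearing date and returning lesions name no body site, although IGA and lesion counts are facial and subjects may have acne elsewhere

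*Protocol*

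**What the plan says.** **Investigator measures are facial.** The Synopsis states that "efficacy assessment by IGA will be limited to the face as that is the most frequent site of involvement", and Section 9.1.1 repeats this. Section 11.1 goes further: "Drug treatment and efficacy assessment by IGA will be limited to the face". For lesion counts, the Synopsis says "Inflammatory and noninflammatory lesions on the face will be counted and reported separately", and the row in Table 4.a carries the label Face.

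**Non-facial acne is allowed.** Inclusion criterion 2 (Section 8.1) requires facial acne and adds: "Subjects may also have acne at other body sites".

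**Patient-reported outcomes count as efficacy.** The Synopsis lists them among the criteria for clinical efficacy, and Section 7 names them beside IGA as the basis for judging efficacy in Part B.

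**Appendix A names no site.** The weekly block asks how the subject's rash has changed since the previous visit, then "On approximately what date did the Acne Vulgaris clear", then whether cleared lesions have returned. The last-visit block repeats these items, with its clearing questions worded for rosacea. None mentions the face.

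**Clearing elsewhere in the protocol.** Part B objective 4 is "Determine the time to full clearing of Acne Vulgaris after initiation of treatment with BMX-010". Objective 3 speaks of "full or partial clearing (final IGA score of 1 or 0", and Section 7.2.1 begins its dose-stopping rule with "If the Acne Vulgaris is deemed as cleared by the study investigator (IGA=0".

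**The concern.** Two sets of efficacy data are collected at the same visits, and they need not describe the same skin. The investigator looks at the face. The subject is asked about the acne or the rash and may answer for the whole body. For a subject with acne only on the face this makes no difference. For a subject who also has trunk acne, the two sources can disagree although neither is in error.

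What is at stake is how well the patient-reported results can be interpreted. In Part B, randomisation balances non-facial acne between the arms on average, so the mixing does not by itself favour one arm. It adds noise, and it weakens the patient-reported contrast if the other sites respond less than the face. It also makes the reported clearing dates hard to set against the visits at which IGA reached 0.

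**Working it through.** The protocol gives no figure to reproduce, so the check is a comparison of passages.

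| Item | Who reports | Site |
|---|---|---|
| IGA (Synopsis, 9.1.1, 11.1) | Investigator | Face |
| Lesion counts (Synopsis, Table 4.a) | Investigator | Face |
| Cleared acne, dose-stopping rule (7.2.1) | Investigator, IGA 0 | Face, through IGA |
| Change since previous visit (Appendix A) | Subject | Not stated |
| Date of clearing (Appendix A) | Subject | Not stated |
| Return of cleared lesions (Appendix A) | Subject | Not stated; a new area is to be specified |

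Take a subject whose face reaches IGA 0 at Day 22 while acne on the back is still active.

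1. **IGA:** cleared at Day 22.
2. **Clearing date:** the block is asked after full or partial clearing, so this subject should be asked. Answering for the face gives a date up to Day 22. Answering for the whole body gives a later date or none.
3. **Change:** answering for the face could give the top category. Answering for the whole body could give a lower one.
4. **Return of lesions:** a lesion in a new area has its location written down. One in the same area as before does not.

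For steps 2 and 3 the form has no site field. Table 4.a has no dedicated item for non-facial acne at Baseline either, so the subjects at risk of mixed answers could not be reliably identified later.

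**Size, for illustration only.** Apart from the maximum of 100 subjects on BMX-010 (Section 9.1.1), every rate below is assumed, because the protocol gives none.

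Subjects facially clear but not clear at all sites = N × P(face clear) × P(non-facial acne) × P(persists elsewhere)

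- Facially clear by Day 43: 100 × 0.10 = 10
- Low case: 10 × 0.20 × 0.50 = 1
- High case: 10 × 0.60 × 1.00 = 6
- No non-facial acne: 10 × 0 = 0

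These are subjects who could answer differently. Those who read the question as facial would not, so each figure is an upper limit under its own assumptions.

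**The case against.** The strongest reply is that the protocol is already facial in context. Inclusion criterion 2 defines the study disease as facial acne. Sections 7.1 and 7.2 mention full clearing, as judged by the investigator, just after describing application to the face. Objective 3 equates clearing with IGA 0 or 1, and Section 7.2.1 equates cleared with IGA 0. This stands, and it settles the investigator side.

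A reader might infer that objective 4 has no defined event, or that its event and date differ by source. The documents do not support that. No passage makes the Appendix A date the source for objective 4, and Section 14 leaves the definition of analysis variables to the SAP, where the source may properly be fixed.

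A reader might also infer that a face-clear subject with trunk acne would correctly mark the clearing block as not applicable. That misreads the form: not applicable is for no clearing at all, and this subject has at least partly cleared. Nor is every relapse elsewhere lost, since a new area must be specified.

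Finally, the size is unknown, and the study is exploratory, with sample sizes that have no statistical basis (Section 14.6). That keeps the point small.

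The reply does not cover the wording put to the subject. A SAP can choose a source, but it cannot change what subjects were asked or recover the site they had in mind.

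**Conclusion.** The point holds for the Appendix A items and not for objective 4. The change, clearing-date and come-back questions do not share the facial scope of IGA and the lesion counts, and the first two cannot be separated by site after collection.

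The size cannot be stated from the protocol. It depends on how many subjects have non-facial acne, how often that persists after the face clears, and how many subjects answer for the whole body. If no subject has non-facial acne, it is zero. The illustrative 1 to 6 of 10 facial clearings rests wholly on assumed rates and is not an estimate.

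It would also go too far to say that the extra sites dilute the results because they are untreated. Section 11.1 limits drug treatment to the face, but the Synopsis and Section 9.1.1 let product be used on all affected areas, and footnote 6 of Table 4.a refers to all active lesions. The protocol contradicts itself here, and this review takes no position on which text is right.

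This is a minor, nearly free improvement, but it has to be made before data are collected.

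**What to change.** - **Appendix A:** add *on your face* to the change, clearing-date and come-back items, in both the weekly and the last-visit blocks. The last-visit clearing questions need editing anyway, because they refer to rosacea.
- **Baseline:** record whether the subject has non-facial acne (yes/no), so that it can be described by arm.
- **Objective 4:** adding *facial* and *(IGA = 0)* would be a clarification only.
- **Site of application:** reconcile Section 11.1 with the Synopsis, Section 9.1.1 and footnote 6 of Table 4.a.

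For the first three items the cost is a few words on the form and in the objectives, plus one tick box. The downside is that the patient-reported outcomes would no longer describe body acne, which IGA and the lesion counts do not cover either.

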6.2 Secondary Objectives

Part A

1. Document, as possible, the clinical effects of BMX-010 in subjects with Acne Vulgaris through clinical photography.
2. Assess the mean percent reduction change in inflammatory and noninflammatory lesion counts from baseline to end of study.

Part B

1. Determine the percent of subjects showing a 1 grade improvement in the IGA score.
2. Document, as possible, the clinical effects of BMX-010 in subjects with Acne Vulgaris through clinical photography.
3. Assess the mean percent reduction change in inflammatory and noninflammatory lesion counts from baseline to end of study.

7 STUDY DESIGN

The purpose of this study is to first explore the optimum formulation (gel vs. cream), concentration (0.03% vs. 0.1%), and dosing frequency (QD vs. BID) of BMX-010 in subjects with Acne Vulgaris in Part A. In Part B, the optimal formulation, concentration, and frequency will be used to study the efficacy of BMX-010, as determined by IGA scores and PROs.

[figure not shown]
7.1 Part A Study Design

Subjects will be dispensed either 0.03% BMX-010 or 0.1% BMX-010 (gel or cream), at the discretion of the clinical center investigator, to apply to Acne Vulgaris on the face. Topical therapy with BMX-010 will be either QD or BID, also at the discretion of the clinical center investigator. The planned treatment duration is a minimum of 7 days and a maximum of 28 days. Completion of 28 days of treatment will be recommended to all subjects; however, subjects who have full clearing of the Acne Vulgaris, as determined by the clinical center investigator, may stop study drug therapy and remain in the study with a final evaluation at Day 29 or Day 43 (at the discretion of the investigator).

7.2 Part B Study Design

Subjects will be randomized 2:1 to receive topical administration of BMX-010 or Placebo which will be dosed at the concentration, formulation, and frequency as defined by Part A. Study product will be applied liberally to Acne Vulgaris on the face. The planned treatment duration is a minimum of 7 days and a maximum of 28 days. Completion of 28 days of treatment will be recommended to all subjects; however, subjects who have full clearing of the Acne Vulgaris, as determined by the clinical center investigator, may stop therapy and remain in the study with a final evaluation at Day 29 or Day 43 at the discretion of the investigator. There will be weekly visits with follow-up done at approximately Days 8, 15, 22, 29 and 43.

Figure 7.a Study Design for both parts

Following written informed consent, subjects will undergo screening evaluations within 14 days prior to the first application of study drug. The screening evaluations will include complete medical history, complete physical examination (including vital signs, weight, and height), clinical laboratory evaluations, urine pregnancy test for females of child-bearing potential (a negative pregnancy test is required within 48 hours prior to the start of drug treatment), concurrent medical conditions, and concomitant medication assessments.

Subjects will be scored by the clinician for IGA. The clinician will also obtain counts of the inflammatory and noninflammatory lesions on the face.

The subject will be asked a series of Patient Reported Outcomes (Appendix A).

In **Part A**, all eligible Subjects enrolled will receive the active study drug, BMX-010. Subjects will treat their Acne Vulgaris on the face with the study product. This will be demonstrated at the Baseline visit. Subjects will be instructed by the clinical center staff and informed how often they should dose each day (QD or BID).

In **Part B**, all eligible Subjects enrolled will be randomized to the study drug (BMX-010) or Placebo. Subjects will treat their Acne Vulgaris on the face with the study product. This will be demonstrated at the Baseline visit. Subjects will be instructed by the clinical center staff and informed how often they should dose each day, which will have been confirmed by Part A of the study.

Randomization will occur after completion of all screening assessments, once the subject is determined to be eligible. At Baseline, subjects will undergo confirmation study eligibility assessments as specified in Table 4.a. The first dose of study drug will be administered in the clinic under the supervision and direction of study staff and subjects will be trained on the amount of study product to use and where to apply it.

Subjects will be instructed to bring all study drug (including empty tubes) with them when they return to the clinic each week for assessment of study drug use by the clinical center.

Subjects will be asked a series of questions (Appendix A) during in-clinic study visit days.

Subjects will be able to consent to optional photographs the treated lesions. Since the Acne Vulgaris to be treated is on the face, the photos may include the face.

Throughout both phases, subjects will be queried regarding adverse events (AEs), concurrent medical history, and concomitant medication usage.

